## NON-INTERVENTIONAL (NI) STUDY PROTOCOL

## **Study Information**

Title  Protocol number  Protocol version identifier  Date	Real-World Effectiveness of Tafamidis 80 mg or 61 mg on Neurologic Disease Progression in Patients with Mixed-Phenotype Variant Transthyretin Amyloid Cardiomyopathy (ATTRv-CM) B3461099 v3.0
Active substance	N07XX08
Medicinal product	Tafamidis
Research question and objectives	Primary objective:  • To assess neurologic function before and after initiation of tafamidis, as either VYNDAQEL 80 mg (four 20-mg tafamidis meglumine capsules) orally once daily or VYNDAMAX 61 mg (one 61-mg tafamidis capsule) orally once daily, in patients with mixed-phenotype ATTRv-CM in a real-world setting  Secondary objective:  • To assess modified body mass index (mBMI) in patients with mixed-phenotype ATTRv-CM receiving tafamidis, as either VYNDAQEL 80 mg (four 20-mg tafamidis meglumine capsules) orally once daily or VYNDAMAX 61 mg (one 61-mg tafamidis capsule) orally once daily, in a real-world setting
Author	PPD (Main Author) PPD

## 2. LIST OF ABBREVIATIONS

Abbreviation	Definition		
ANOVA	Analysis of variance		
ATTR-ACT	Transthyretin amyloidosis cardiomyopathy clinical trial		
ATTR-CM	Transthyretin amyloid cardiomyopathy		
ATTR-PN	Transthyretin amyloid polyneuropathy		
ATTRv	Variant transthyretin amyloidosis		
ATTRv-CM	Variant transthyretin amyloid cardiomyopathy		
ATTRwt	Wild-type transthyretin amyloidosis		
BMI	Body mass index		
CCI	Charlson Comorbidity Index		
CMTNS2	Charcot-Marie-Tooth neuropathy score v2		
CI	Confidence interval		
EMR	Electronic medical record		
FTP	File transfer protocol		
GPP	Good pharmacoepidemiology practices		
HIV	Human immunodeficiency virus		
ID	Identifier		
IRB	Institutional review board		
IP	Internet protocol		
ISPOR	International Society for Pharmacoeconomics and Outcomes Research		
mBMI	Modified body mass index		
NIS-CS	Neuropathy impairment score-composite score		
NIS-LL	Neuropathy impairment score-lower limbs		
MMRM	Mixed model repeated measures		
MRC	Medical Research Council		
PND	Polyneuropathy disability		
REDCap	Research Electronic Data Capture		

Abbreviation	Definition	
SAP	Statistical analysis plan	
SAS	Statistical Analysis System	
SD	Standard deviation	
TTR	Transthyretin	
QA	Quality assurance	
QC	Quality control	

## 4. ABSTRACT

Standalone document - Annex 1.

## 5. AMENDMENTS AND UPDATES

Amendment number	Date	Protocol section(s) changed	Summary of amendment(s)	Reason
Amendment 1	01/09/23	1-6, 9, 11	Administrative amendment:  Number and timing of measurements changed to address data availability.  Addition of CMTNS2 instrument.  Updated template language for data analysis  Updated AE reporting language per SOP	Change in PIs and available data. Not expecting most patients to have multiple measures before or after treatment.
Amendment 2	31 May 2023	Inclusion Criteria, Section 9.21	Changed criteria number 4 from "≥2: to "≥1"	Administrative, typographical error
Amendment 2	31 May 2023	Table 9-2, Clinical Outcomes	Deleted footnote to align with SAP	Administrative

#### 6. MILESTONES

Milestone	Planned date
Completion of feasibility assessment	30 October 2022
Start of data collection	28 February 2023
End of data collection	01 November 2023
Final study report	01 October 2024

#### 7. RATIONALE AND BACKGROUND

ATTR amyloidosis is a progressive, life-threatening, and heterogeneous rare disease caused by the deposition of transthyretin-derived amyloid fibrils in the peripheral nerves, heart, and other organs.  ATTR amyloidosis may arise from variants (mutations) in the transthyretin (TTR) gene (ATTRv amyloidosis), with more than 140 ATTRv genotypes having been identified,  or from the aggregation of non-mutated wild-type TTR (ATTRwt amyloidosis). Amyloid deposition in the peripheral nerves results in transthyretin amyloid polyneuropathy (ATTR-PN), but multiple symptoms and system involvement are hallmarks of ATTR-PN.  Amyloid fibril deposition in the extracellular matrix of the heart  results in ATTR-CM, which is characterized by arrhythmias and heart failure.  ATTRwt amyloidosis predominantly manifests as ATTR-CM. ATTRv amyloidosis is now widely recognized as a spectrum of disease that can manifest as polyneuropathy, cardiomyopathy, or a mixed phenotype, depending on the particular TTR variant, amyloid deposition pattern, and multisystem involvement.

Tafamidis meglumine is a first-in-class highly specific and selective stabilizer of both wild-type and amyloidogenic variants of transthyretin (TTR) developed for the treatment of ATTR amyloidosis.  Tafamidis binds to TTR at the thyroxine-binding site and inhibits TTR tetramer dissociation, the rate-limiting step in the amyloidogenic process. By stabilizing the tetrameric native state of TTR, tafamidis increases the activation barrier associated with tetramer dissociation and therefore mimics the tetrameric-stabilization effect observed with naturally occurring protective trans-suppressor variants. Tafamidis has been extensively studied for the treatment of ATTR amyloidosis in independent development programs in ATTR-PN and ATTR-CM.

Tafamidis meglumine 20 mg was the first disease-modifying therapy approved for the treatment of ATTR-PN and is currently labeled and approved for once-daily dosing for treatment of transthyretin amyloidosis in adult patients with stage 1 symptomatic polyneuropathy to delay peripheral neurologic impairment. Available in over 40 countries worldwide (excluding the United States) and marketed as VYNDAQEL, tafamidis meglumine 20 mg for treating ATTR-PN has demonstrated efficacy and safety and is backed

by a clinical development program including 1 controlled and 4 uncontrolled studies  The long-term effectiveness and safety of tafamidis in ATTR-PN has been further confirmed in real-world clinical practice, where it significantly delayed disease progression and improved overall quality of life.  As ATTR-PN is a progressive disease, early diagnosis and treatment are paramount,  although there are patients who continue to progress despite treatment.  In a real-world retrospective cohort study of 210 patients with hereditary ATTR amyloidosis treated with tafamidis meglumine 20 mg, tafamidis concentration (and consequently TTR kinetic stabilization) was identified as a predictor of response in a subset of patients, fueling the speculation that ATTR-PN patients might benefit clinically from a higher dose of. 

Tafamidis delivered as either VYNDAQEL 80 mg (four 20-mg tafamidis meglumine capsules) orally once daily or VYNDAMAX 61 mg (one 61-mg tafamidis capsule) orally once daily was the first disease-modifying therapy approved for the treatment of cardiomyopathy of wild-type or hereditary transthyretin-mediated amyloidosis in adults to reduce cardiovascular mortality and cardiovascular-related hospitalization. Tafamidis is currently approved for the treatment of ATTR-CM in approximately 54 countries worldwide (including the United States). The efficacy and safety of tafamidis for treating ATTR-CM are supported by a clinical development program including one controlled and two uncontrolled studies in patients with ATTRv and ATTRwt cardiomyopathy. 21-23 The pivotal study of tafamidis in ATTR-CM, known as ATTR-ACT, examined 20 mg and 80 mg (4 x 20 mg) of tafamidis meglumine with active dose groups pooled and compared with placebo for primary and secondary efficacy analyses. Both tafamidis doses significantly reduced the combination of all-cause mortality and cardiovascular-related hospitalizations over 30 months versus placebo. The individual 20-mg and 80-mg doses were further examined in post-hoc analyses of 30-month data from ATTR-ACT and interim data from the ongoing open-label long-term extension of ATTR-ACT. After a median of 51 months' follow-up, patients initially treated with tafamidis 80 mg had a significant survival benefit compared with those initiated on the 20-mg dose. However, neurologic endpoints were not evaluated in the ATTR-CM development program, necessitating the use of alternative approaches to assess the potential benefit of tafamidis, as either VYNDAQEL 80 mg (four 20-mg tafamidis meglumine capsules) orally once daily or VYNDAMAX 61 mg (one 61-mg tafamidis capsule) orally once daily for delaying neurologic disease progression in ATTR amyloidosis.

Real-world data collection offers one such alternative. There are ATTRv-CM patients treated with tafamidis, as either VYNDAQEL 80 mg (four 20-mg tafamidis meglumine capsules) orally once daily or VYNDAMAX 61 mg (one 61-mg tafamidis capsule) orally once daily, who are mixed phenotype and receiving cardiologic and neurologic assessments prior to and following treatment as part of standard clinical practice. This provides the opportunity to examine the effect of tafamidis, as either VYNDAQEL 80 mg (four 20-mg tafamidis meglumine capsules) orally once daily or VYNDAMAX 61 mg (one 61-mg tafamidis capsule) orally once daily, on neurologic disease progression in these mixed-phenotype ATTRv-CM patients.

#### 8. RESEARCH QUESTION AND OBJECTIVES

## Primary Objective:

 To assess neurologic function before and after initiation of tafamidis, as either VYNDAQEL 80 mg (four 20-mg tafamidis meglumine capsules) orally once daily or VYNDAMAX 61 mg (one 61-mg tafamidis capsule) orally once daily, in patients with mixed-phenotype ATTRv-CM in a real-world setting.

#### Secondary Objective:

[figure not shown]
 To assess mBMI in patients with mixed-phenotype ATTRv-CM receiving tafamidis, as either VYNDAQEL 80 mg (four 20-mg tafamidis meglumine capsules) orally once daily or VYNDAMAX 61 mg (one 61-mg tafamidis capsule) orally once daily, in a real-world setting.

#### 9. RESEARCH METHODS

## 9.1. Study Design

This will be an observational, retrospective cohort study using structured secondary anonymized data. Patients with mixed-phenotype ATTRv-CM receiving tafamidis, as either VYNDAQEL 80 mg (four 20-mg tafamidis meglumine capsules) orally once daily or VYNDAMAX 61 mg (one 61-mg tafamidis capsule) orally once daily for at least 6 months, will be identified. Relevant data will be extracted through at least 6 months following the initiation of tafamidis treatment.

Figure 9-1 Overview of Study Design

\*Charcot-Marie-Tooth neuropathy score v2 (CMTNS2); mBMI: Modified body mass index; MRC: Medical Research Council; NIS-CS: Neuropathy impairment score-composite score; NIS-LL: Neuropathy impairment score-lower limbs; PND: Polyneuropathy disability.

#### 9.2. Setting

The study will include patients with mixed-phenotype ATTRv-CM who are treated with tafamidis, as either VYNDAQEL 80 mg (four 20-mg tafamidis meglumine capsules) orally once daily or VYNDAMAX 61 mg (one 61-mg tafamidis capsule) orally once daily. All patients meeting the study enrollment criteria will be included.

#### 9.2.1. Inclusion Criteria

Patients must meet all the following inclusion criteria to be eligible for inclusion in the study:

- 1. Age ≥18 years at diagnosis.
- 2. Diagnosed with ATTRv-CM, mixed phenotype.
- 3. Treated with tafamidis (VYNDAQEL 80 mg [four 20-mg tafamidis meglumine capsules] orally once daily or VYNDAMAX 61 mg [one 61-mg tafamidis capsule] orally once daily) for ≥6 months.
- 4. Have had ≥1 pre- and ≥1 post-treatment neurologic assessments.\*

\*The pre-treatment neurological assessment will be at least 6 and up to 12 months prior to treatment initiation. The baseline assessment will be within 3 months before or 3 months after the start of tafamidis treatment. In the absence of baseline data within a+/-3 month window, structured data from exam notes may also be retrieved if available to align with real world practice. The post-treatment period will be at least 6months after treatment initiation.

Note: As this study involves anonymized structured data, which according to applicable legal requirements do not contain data subject to privacy laws, obtaining informed consent from patients is not required.

## 9.2.2. Exclusion Criteria

Patients meeting any of the following criteria will be excluded from the study:

- 1. History of organ transplant.
- 2. Wild-type TTR genotype.
- 3. Individuals who are non-ambulatory.
- 4. Prior treatment with any disease-modifying therapy (investigational or approved) alone or in combination, except tafamidis, as either VYNDAQEL 80 mg (four 20-mg tafamidis meglumine capsules) orally once daily or VYNDAMAX 61 mg (one 61-mg tafamidis capsule) orally once daily.
- 5. Peripheral neuropathy attributed to causes other than ATTR amyloidosis (eg, diabetes mellitus, B12 deficiency, HIV infection).

## 9.3. Variables

## 9.3.1. Exposure Variables

Tafamidis treatment will be described using the variables in the table below.

**Table 9-1 Exposure Variables** 

Variable	Role	Data source(s)	Operational Definition
Time to treatment initiation	Exposure	Research database	Calculated as time from ATTR-CM diagnosis to tafamidis initiation
Treatment start date	Exposure	Research database	Date of tafamidis treatment initiation
Treatment end date	Exposure	Research database	Date of end of tafamidis treatment
Treatment duration	Exposure	Research database	Calculated as time from treatment initiation to the end of treatment or last visit date

## 9.3.2. Outcome Variable

For the primary and secondary objectives, the following clinical outcomes will be assessed. Neurologic progression scores are routinely collected in clinical practice.

**Table 9-2 Clinical Outcomes** 

Variable	Role	Data source(s)	Operational Definition
Neurologic progression			
Neuropathy impairment score– composite score (NIS-CS)	Outcome	Research database	Data contains an assessment score for each muscle group or sensation area for motor strength/weakness, muscle stretch reflexes, and sensation. A final NIS-CS score will be calculated as a sum of these scores from the 3 sections ranging from 0 (normal) to 244 (total impairment).
Neuropathy impairment score-lower limbs (NIS- LL)	Outcome	Research database	Same as above, NIS-LL will be calculated using individual assessment scores for motor strength/weakness, muscle stretch reflexes and sensation, from lower body only, ranging 0 (normal) to 88 (total impairment).
Polyneuropathy disability (PND) score	Outcome	Research database	A scoring system of the patient's walking capacity. It consists of four stages from stage 0 (no impairment) to stage IV (confined to a wheelchair or bedridden).
Medical Research Council (MRC) Scale for Muscle Strength	Outcome	Research database	The MRC scale of muscle strength uses a score of 0 to 5 to grade the power of a particular muscle group in relation to the movement of a single joint
Charcot-Marie-Tooth neuropathy score v2 (CMTNS2)	Outcome	Research database	Composite of nine assessments: symptoms (three items), signs (four items), and neurophysiology (two items). It is designed to measure length-dependent

## Tafamidis B3461099 NON-INTERVENTIONAL STUDY PROTOCOL Amendment 2, Version 3.0, 31 May 2023

Variable	Role	Data source(s)	Operational Definition
			motor and sensory impairment in genetic neuropathies. Each assessment is scored on a $0-4$ point scale, reflecting severity of impairment. Patients are classified as mild (CMTNS $\leq 10$ ), moderate (CMTNS $11-20$ ), or severe (CMTNS $\geq 20$ ).
Overall health			
Height	Outcome	Research database	Height in centimeter or inches
Weight	Outcome	Research database	Weight in kilograms or pounds
Body mass index	Outcome	Research database	Recorded or calculated in kg/m 
Modified BMI (mBMI)	Outcome	Research database	Calculated as the product of BMI in kg/m  and serum albumin in g/L to compensate for peripheral edema.

Patient demographic and clinical characteristics to be assessed are listed in Table 9-3.

Table 9-3 Patient Demographics, Clinical characteristics, and Comorbidities

Variable	Role	Data source(s)	Operational Definition
Patient demographics			
Age	Baseline characteristic	Research database	Patient age at baseline*; age groups will be determined by distribution of age.
Gender	Baseline characteristic	Research database	Male/Female
Race	Baseline characteristic	Research database	American Indian or Alaska Native/Asian/Black or African American/Native Hawaiian or Other Pacific Islander/White
Ethnicity	Baseline characteristic	Research database	Hispanic or Latino/Not Hispanic or Latino
Clinical characteristics			
Age at ATTR-CM diagnosis	Baseline characteristic	Research database	Age at diagnosis in years
TTR genotype	Baseline characteristic	Research database	Mutation in TTR gene associated with ATTR amyloidosis (eg, Val122Ile, Val30Met, Leu58His, Leu111Met)
Family history	Baseline characteristic	Research database	No family history/Parent/Siblings/Grandparent/ Other/Unknown
Comorbidities			
Charlson Comorbidity Index (CCI)**	Baseline characteristic	Research database	Based on comorbidities present at baseline*; grouped as 0, 1, 2, 3+

\*Baseline is defined as within 3 months prior to or 3 months following initiation of tafamidis. In the absence of baseline data within a +/- 3-month window, data outside this window may be used to align with real world practice.

#### 9.4. Data Source

The source of data for this study will be de-identified secondary data from an anonymized research database.

## 9.5. Study Size

No formal sample size calculation has been performed; all eligible patients treated at the study site will be included. It is estimated that at least 30 patients will be enrolled.

## 9.6. Data Management

Data will be transferred from the de-identified research database to OPEN Health's database server via encrypted external hard drive/disk or a secured file transfer protocol (FTP) server, which is locked in a secure room with physical access limited to server administrators. Network access to the database server will be restricted to the internet protocol (IP) addresses of project staff workstations on a limited access network behind a firewall system. Only

\*\*Individual comorbid conditions may be assessed based on feasibility assessment instead of CCI.

authorized personnel as indicated above will be provided with the password to use the media or log in to the server to access the data for analysis. The authorized personnel may download analytical datasets to their secured OPEN Health computers (encrypted and password protected). However, download to any personal computer will not be possible. Access to the received media and printed materials containing EMR data will be restricted to project staff and will be kept in a locked file cabinet. Aggregated analyses results will be presented at conferences and/or published in a journal with no patient-level data exposed.

The data will be used only for this specific study protocol. There will be no linkage of the data with any other data source. Patient IDs in the data are de-identified, and it will be impossible to trace patients' personal information (eg, name, mailing address) by using the patient ID. All analyses will be performed using Statistical Analysis System (SAS) version 9.4.

## 9.7. Data Analysis

Detailed methodology for summary and statistical analyses of data collected in this study will be documented in an SAP, which will be dated, filed, and maintained by the sponsor. The SAP may modify the plans outlined in the protocol; any major modifications of primary endpoint definitions or their analyses will be reflected in a protocol amendment.

## 9.8. Quality Control

To ensure programming quality and accuracy, the following steps will be taken:

- **Methodology review:** All methodology, from sample selection to variable calculation, will be discussed and reviewed at the time of project initiation.
- Operational definitions review: All operational definitions for calculated variables will be reviewed by the principal SAS programmer, a second SAS programmer, and Pfizer.
- Statistical review: The statistical methods utilized will be reviewed by a statistician
  as well as the SAS statistical programmer, project manager, senior scientific leader,
  and Pfizer.
- Output review: All SAS output will be initially reviewed by the SAS programmer for logic and reasonability. Output will then be reviewed by the project manager, senior scientific leader, and Pfizer. Additional reports will be run by the SAS programmer and Pfizer to ensure validation of SAS output.

During document preparation, quality control (QC) will include general proofreading and formatting, including but not limited to checks for errors related to spelling and grammar, font consistency, table/figure numbering, styles/header numbering, and general formatting/spacing. QC will also include confirming data (fact checking) and ensuring proper referencing, when applicable. For analyses and reports that utilize technical software, QC

will additionally include cross-checking internal methods/statistical review and ensuring clear presentation of findings. A corrective and preventative action plan will be part of analytic projects, with a documented deviation process and mechanisms in place to report serious deviations on the quality of/processes generating the data. The project officer or non-project senior staff member will serve as the internal resource for investigating and reporting serious deviations. The QC/quality assurance (QA) procedure will also be conducted for written communications, including meeting minutes and project-related emails, with internal team members and Pfizer.

#### 9.9. Limitations of the Research Methods

This study will have several limitations.

First, the retrospective and observational nature of our study may be subject to unmeasured confounding. However, a longitudinal before and after study design will be used to evaluate treatment effects in the same patient group. It will also be unlikely to have unmeasured time-varying patient factors since ATTR-CM is an inexorably progressive disease caused by genetic mutation or the aggregation of non-mutated, wild-type TTR due to aging. Study results could be affected by misclassification bias due to misreporting or misdiagnosis due to the similarity of ATTR-CM to other types of heart failure.

Second, the study will be limited to ATTRv-CM patients from a single center, potentially mitigating generalization of study results to other ATTRv-CM patient populations due to different patient characteristics or local practice patterns.

Finally, ATTR-CM is a rare disease. While the inclusion of <100 patients is generally considered a relatively small sample size, it is not for a rare disease. The sample size of the previous clinical trial that established the efficacy of once-daily tafamidis 20 mg on delaying neurologic progression in ATTR-PN was also relatively small given that this is a rare disease.  In addition, as the study will be exploratory in general, the sample size is not expected to be a limiting factor, and this will be taken into account when reporting the results.

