#### 7.2. Statistical Analyses

For the primary and secondary objectives, neurologic function, ie, NIS-CS, NIS-LL, MRC, CMTNS2, and mBMI will be examined in the full analysis set. If there is a sufficient number of patients with at least three neurologic assessments a linear mixed-effect model will be conducted to compare the rate of disease progression (within patient) between pre-treatment and tafamidis treatment periods. Patients must have at least three assessments to be included in the linear mixed-effect model (one in the pre-treatment period, one in the tafamidis treatment period, and one additional that can be in either pre-treatment or in the tafamidis treatment period). The linear mixed-effect model includes pre-treatment baseline score, treatment period, and their interactions with time as fixed effects, and the time-slope and intercept for each patient are included as random effects. Time is defined as number of months from pre-treatment baseline. The estimates of the monthly rate of change, along with the 95% confidence interval and the p value associated with the within group comparison comparing the pre-treatment and tafamidis treatment periods will be summarized.

However, if there is not a sufficient number of patients with at least three neurologic assessments, and many patients only have two assessments, then an approach is to take the first measurement and the measurement that fell within the window of the measurement in which majority of the patients had for the post-treatment assessment (whether they only have two or three or more) and test for significant statistical differences between the two assessments using an unpaired, or independent samples, t-test.

Alternatively, in the event there is an insufficient number of patients with three or more neurologic assessments, separate subgroup statistical analyses may be performed. This approach may use a between-subjects analysis of variance (ANOVA) for patients with at least three neurologic assessments and conduct unpaired, or independent samples, t-test for

patients with only two neurologic assessments. Descriptive summaries will be provided by treatment (pre-treatment or post-treatment), or by subgroups (if data permits) for each neurologic function endpoint.

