It is anticipated that there will be patients who do not satisfy inclusion criteria for pre and post treatment comparisons for various reasons such as not being on treatment for at least 6 months (with ±3-month window) because they passed away, not having a pre-treatment or post-treatment neurologic assessment, not having a NIS score or other missing data points and/or reasons. While pre and post treatment comparisons cannot be conducted for these patients, descriptive statistics on the composite score and/or its sub-scale will be reported to characterize patient and treatment characteristics.

Additional post-hoc analyses of final data from this study may be performed against final data from comparable tafamidis-treated and untreated ATTRv mixed phenotype patients from the Transthyretin Amyloidosis Outcomes Survey (THAOS; Pfizer Study B3461001). If performed, analysis methods will be provided as part of an amendment to this SAP.

All data analysis will be executed using statistical software SAS version 9.4.

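### Protocol 9.9 argues from steady progression to an absence of time-varying confounding; the before-after contrast isolates a drug effect only if the untreated rate stays constant, which neither document states

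*Protocol*

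**What the plan says.** Protocol 9.9 opens with a concession: "First, the retrospective and observational nature of our study may be subject to unmeasured confounding". It then offsets this by saying that "a longitudinal before and after study design will be used to evaluate treatment effects in the same patient group", and adds: "It will also be unlikely to have unmeasured time-varying patient factors since ATTR-CM is an inexorably progressive disease caused by genetic mutation". The sentence goes on to mention wild-type disease due to ageing as the other cause.

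SAP 7.2 plans, if enough patients have three assessments, a linear mixed model to "compare the rate of disease progression (within patient) between pre-treatment and tafamidis treatment periods". Its terms are given as: "The linear mixed-effect model includes pre-treatment baseline score, treatment period, and their interactions with time as fixed effects". Each patient also has a random intercept and slope. The clock is set by: "Time is defined as number of months from pre-treatment baseline".

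If too few patients have three assessments, SAP 7.2 would test the first measurement against a post-treatment measurement with an unpaired t-test. A further option uses between-subjects ANOVA for patients with three or more assessments and the same t-test for those with two.

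The only comparison with untreated patients is optional: "Additional post-hoc analyses of final data from this study may be performed against final data from comparable tafamidis-treated and untreated ATTRv mixed phenotype patients". Its methods are left to a later SAP amendment.

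SAP 3.1 calls all analyses exploratory, without formal hypothesis testing, but keeps p-values at the 0.05 level.

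**The concern.** Progression is a process that changes with time, and by construction it is aligned with the treatment contrast: every patient is further along in the disease on tafamidis than before it. That a disease progresses inexorably is therefore no reason to expect time-varying factors to be absent. What the argument needs is that the untreated rate would not have changed, which is a different and stronger statement.

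The sentence also fits this study poorly. It appeals partly to wild-type disease, which exclusion criterion 2 removes, and it argues from the cardiac disease while the primary endpoint is neurologic.

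At stake is what the study may conclude. A study titled as one of effectiveness, with a limitations section that discounts the main rival explanation, invites readers to take a change in slope as a drug effect. A natural acceleration could equally hide a benefit.

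**Working it through.** There is no figure in the plan to reproduce: no effect size, SD or natural-history rate is given, and the sample size of at least 30 is an estimate. The check sets the true drug effect to zero and asks what each planned analysis would show. All rates and SDs below are assumptions, in score points and months.

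**1. What the slope contrast measures.** Take visits at −L, 0 and +L months from initiation and an untreated course y = a + bt + ct².
- Pre-treatment slope: [y(0) − y(−L)]/L = b − cL
- Treated slope: [y(L) − y(0)]/L = b + cL
- Difference: 2cL

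With c = 0 the difference is zero whatever b is, so constant progression drops out. With L = 9 and c = ±0.01 it is 2 × (±0.01) × 9 = ±0.18 per month.

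**2. How often that would look significant.** Simulated within-patient slope contrast: three visits 9 months apart, n = 30, between-patient slope SD 0.2, 20,000 runs.

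| Untreated rate, before → after | Mean difference | p < 0.05, residual SD 4 | p < 0.05, residual SD 2 |
|---|---|---|---|
| 0.5 → 0.5 | about 0 | 5% | 5% |
| 0.5 → 0.25 | −0.25 | 23% | 68% |
| 0.25 → 0.5 | +0.25 | 23% | 68% |

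The two lower rows mirror each other: one would be read as benefit, the other as harm.

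**3. The SAP 7.2 model itself.** Fitted with the stated fixed and random effects, two visits per period, residual SD 2, n = 30, 150 runs:
- 0.5 → 0.5: mean estimate −0.006, significant in 9% of runs (imprecise with 150 runs)
- 0.75 → 0.25: mean estimate −0.47
- 0.5 → 1.0: mean estimate +0.46

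The model neutralises a constant rate and passes a natural change of ±0.50 through almost whole.

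**4. Direction is not fixed by the bounded scale.** Take NIS-LL (0 to 88) at 30 points and 1 per month at initiation, visits at −9, 0 and +9.
- Rate proportional to (88 − score): 1.082 before, 0.926 after, a change of −14.4%
- Logistic course on the same scale: 0.918 before, 1.058 after, a change of +15.3%

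Same inputs, opposite signs.

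**5. The two-assessment fallback.** This compares levels. At a constant untreated rate r and a gap of g months, the expected difference is r × g. The pre-treatment visit lies 6 to 12 months before initiation. If the post-treatment window is read as 6 ± 3 months, the gap runs from 6 + 3 = 9 to 12 + 9 = 21 months. At r = 0.5 that is 4.5 to 10.5 points with no change in rate at all. At g = 18 the difference is 0.5 × 18 = 9 points. With 30 values per time point, treated as independent as the unpaired test does, it would be significant with probability 0.41 (SD 20) to 0.64 (SD 15).

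The fallback is a realistic branch: Protocol Section 5 gives as a reason for Amendment 1 that most patients are not expected to have multiple measures before or after treatment.

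**The case against.** The best defence is that the plan claims little. Section 9.9 concedes unmeasured confounding and calls time-varying factors unlikely, not absent. The primary objective is descriptive, the analyses are labelled exploratory, and the model handles constant progression and between-patient differences in rate. All of that is correct. It softens the problem without curing it, because the caveat is offset by the sentences that follow it, treatment effects are named as the target, and p-values at 0.05 remain.

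Several stronger readings are tempting, and the documents do not support them:
- *Any slowing will be credited to tafamidis.* No passage commits the sponsor to that conclusion.
- *The bias favours tafamidis because the scales have a ceiling.* Step 4 shows that the sign depends on the assumed curve. Non-ambulatory patients are excluded, which limits near-ceiling scores, and PND is not among the endpoints listed for the SAP 7.2 analysis.
- *Treatment was started because of neurologic worsening, which inflates the pre-treatment slope.* No passage says so, and the protocol describes this dose as approved for cardiomyopathy.
- *Rates are known to differ in shape by variant.* The background says that the manifestation depends on the variant. It says nothing about linearity.
- *Exclusion 5 proves that new causes of neuropathy will confound.* It excludes "Peripheral neuropathy attributed to causes other than ATTR amyloidosis (eg, diabetes mellitus, B12 deficiency, HIV infection"), so it is partial mitigation.

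**Conclusion.** The point holds as a flaw in reasoning and in the stated scope of inference. Section 9.9 claims for the before-after contrast a protection that the design does not have. The slope contrast equals a drug effect only under a constant untreated rate in each patient, an assumption neither document states or defends. The fallback level comparison cannot separate tafamidis from ordinary progression even under that assumption.

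The size cannot be derived from the documents. The calculations show the mechanism and that plausible-looking changes in rate would matter at n = 30. They do not estimate the actual bias, and its direction is open. The finding does not say that tafamidis lacks a neurologic effect or that the mixed model is the wrong model. It should be corrected before reporting, because it alters what the study can conclude.

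**What to change.** 1. In Protocol 9.9, delete the sentence on time-varying factors. State instead that the slope contrast assumes each patient's untreated rate would have stayed constant, and that the fallback level comparison cannot separate tafamidis from ordinary progression.
2. In Protocol 9.9 and SAP 7.2, word the conclusion as change in rate (or in level) after initiation, and do not call it a treatment effect.
3. If the comparison with untreated registry (THAOS) patients will be used to support effectiveness, file its SAP amendment before the before-after results are seen. The SAP already requires the amendment; only its timing is new.

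A quadratic natural-course term is not part of the request. With three visits per patient it cannot be told apart from a slope change within a patient, so it would lean on between-patient differences.

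The cost is wording in two documents and, if the registry comparison is used, earlier work on its methods. No new data are needed from study patients. The downside for the sponsor is a less favourable conclusion statement.
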